# RESEARCH PLAN

## A) SPECIFIC AIMS

Treatment recommendations for polycystic ovary syndrome (PCOS) in adolescent girls are based on very few studies and mainly expert opinion. Therefore more studies are needed on therapeutic regimens that improve the wellbeing of adolescent girls suffering from this condition. Targeted intervention that addresses the core metabolic disturbance in PCOS may also provide much needed information about the interconnectivity between signs, symptoms, and diagnostic parameters. The current proposal will provide preliminary data on a novel treatment paradigm for adolescent PCOS as well as important pilot information on neuro-endocrine connection in PCOS.

**Hypothesis:** A 6-month trial of synergistic combination drug therapy with low dose insulin sensitizer (metformin) and anti-androgen (spironolactone) will significantly improve metabolic profile and clinical manifestations of PCOS in adolescents.

**Specific Aim 1:** To examine the effects of a 6-month drug intervention with combined low dose metformin (500mg orally BID) and spironolactone (50 mg orally QD) in adolescent PCOS on biochemical markers of insulin resistance such as the whole-body insulin sensitivity index (WBISI). The WBISI will be calculated from glucose and insulin values obtained during the oral glucose tolerance testing (OGTT) before and after drug intervention.

While improving insulin resistance is an important metabolic target, most patients are concerned with central adiposity, which is linked to insulin resistance. To this end, studies have demonstrated reduction in body mass index (BMI), and an improvement in waist-hip circumference in women treated with metformin. Therefore, secondary treatment outcomes will not only include lipid profile and other biochemical markers of PCOS but also include changes in body composition as assessed by bio-impedance scale. Further clinical outcome measures will include menstrual cycle regularity, ovarian morphology changes as assessed by trans-abdominal ultrasound, hirsutism scores and resting blood pressure.

**Specific Aim 2:** To examine structural and functional brain changes associated with adolescent PCOS before and after drug intervention designed to improve insulin resistance.

In adolescents, improving insulin resistance with metformin was recently attributed to reduced food intake with decreased perceived hunger. Therefore, our second aim may lead to a mechanistic understanding of why adolescent with PCOS often improve BMI with improved insulin resistance. Indeed, it has been postulated that insulin resistance not only affects diabetes and cardiovascular disease but exerts a significant impact on central nervous system (CNS) function regarding neuro-functional responses to food-related cues. Insulin resistant women with PCOS show a differential brain response to glucose challenge testing. These authors hypothesize this could lead to increased caloric intake and eating past the point of satiety (non-homeostatic eating). Since food intake is also a function of mood, a standard depression questionnaire will be administered.

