## **RESEARCH DESIGN AND METHODS**

### **Research Design and Procedures:**

The overall objective of this proposal is to determine if metabolic improvements occurs in adolescents with PCOS after a 6-month open label intervention with a low dose synergistic drug regimen of metformin (insulin sensitizer) and spironolactone (anti-androgen).

Initial data will be collected as part of the patient’s routine PCOS health care. Should a patient consent to the study this data will be used as baseline analysis. During the 6- month intervention study the subject will have a safety monitoring visit at 3 months into the intervention which will include blood work, complete examination and compliance history. All baseline examinations will be covered by insurance. All post intervention biochemical or other testing will be covered by study funds and [name] neuro-imaging start-up funds.

For complete study design: see flow chart at end of the RESEARCH DESIGN AND METHODS section.

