**Drugs/Experimental Intervention:**

Subjects will receive 6 months combination drug therapy with a combination of low dose metformin and spironolactone.

Intervention – Metformin: The investigational pharmacy will distribute the metformin. The study dose will be 500 mg/tab orally BID, to be taken with food at breakfast and dinner. In order to improve tolerability of the regimen, the drug will be started sub-therapeutically. The first 4 days only ½ tablet will be taken with dinner and then increased to 1 tab for the next 3 days with dinner. The second week ½ tablet will be added to breakfast for four days and then the next 3 days the breakfast dose is increased to 1 tablet. After two weeks the subject will be on 500 mg BID from which time the 6- month intervention is counted. Long term use of metformin may lead to vitamin B12 deficiency. Therefore, vitamin B12 levels will be measured in the study and balanced diet is recommended.

Intervention - Spironolactone: The investigational pharmacy will distribute the spironolactone. The subject will take one tablet (50mg/tab orally QD) with breakfast once the metformin dose has been titrated up to 500 mg BID, approximately 2 weeks into the study. The 6-month intervention counts from the first dose of spironolactone taken.

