## **DATA Collection**

Research material will be obtained through from their medical record for laboratory test results including OGTT, anthropometric measures, ultrasound data, vital signs, physical examination, including hirsutism score and birth history, medical history, family history and menstrual history will also be collected. Further materials include a depression score.

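### Could Aim 2's baseline brain scan fall after metformin has started, so that the plan must fix its timing or drop the aim?

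*Combined protocol and SAP*

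**What the plan says.** Specific Aims states Aim 2 as: "To examine structural and functional brain changes associated with adolescent PCOS before and after drug intervention designed to improve insulin resistance". Its rationale is partly a metformin effect, since in adolescents "improving insulin resistance with metformin was recently attributed to reduced food intake with decreased perceived hunger". The same paragraph adds: "Since food intake is also a function of mood, a standard depression questionnaire will be administered".

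Drugs/Experimental Intervention has metformin stepped up over two weeks. Spironolactone is added "once the metformin dose has been titrated up to 500 mg BID, approximately 2 weeks into the study". The duration rule is: "The 6-month intervention counts from the first dose of spironolactone taken". The metformin paragraph counts the six months from the same point, when the full study dose is reached.

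Research Design and Procedures takes baseline data from routine PCOS care. On funding it says "All baseline examinations will be covered by insurance" and "All post intervention biochemical or other testing will be covered by study funds and [name] neuro-imaging start-up funds". It then refers the reader to a flow chart for the complete design. Preliminary Studies names the OGTT and the ovarian ultrasound as tests done at every patient's initial consultation; it does not mention a brain scan.

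**The concern.** Aim 2 is a within-person contrast, so it depends on a first scan taken before any drug effect. Two rules seem not to secure that.

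- **The count.** If 'before' meant before the counted six months, the first scan could fall after two weeks of metformin, the drug to which the rationale attributes reduced hunger. An early effect in the same direction as the later one would shrink the estimated change, and a missed pre-drug scan cannot be recovered.
- **The baseline rule.** Routine-care data paid for by insurance suit the OGTT and ultrasound, but fit a research scan poorly. Imaging funds are named only alongside post-intervention testing.

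The depression questionnaire, introduced in the same rationale, is carried through the protocol (DATA Collection: "Further materials include a depression score"), while the scan is not. If paired scans were not planned at all, Aim 2 could not be answered and follow-up scans alone could not be reported as change.

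**Working it through.** **1. The plan's own power figure.** Data Analysis gives n = 20, means 4.7 and 8.0, SD of change 4.0 and two-sided alpha 0.05. For a paired t-test, df = 19 and the noncentrality is (3.3/4.0) × √20 = 3.69. Power is 93.8%, against 93% stated, so the figure reproduces. It concerns the insulin sensitivity index only and does not depend on when a scan is done. No figure is stated for Aim 2.

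**2. Size of the gap before the count starts**, from the titration schedule:

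| Days | Daily metformin (mg) | Total (mg) |
|---|---|---|
| 4 | 250 | 1,000 |
| 3 | 500 | 1,500 |
| 4 | 750 | 3,000 |
| 3 | 1,000 | 3,000 |
| 14 | mean 607 | 8,500 |

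That is 8,500/14,000 = 61% of 14 days at 1,000 mg/day. The 14 days are 14/182.6 = 7.7% of six months.

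**3. What an on-drug first scan could cost.** Let f be the share of the six-month change already present at two weeks. The observed change is then (1 − f) × the true change. Take a true change of 0.66 SD, chosen because it gives 80% power with 20 pairs (two-sided 0.05):

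| Assumed f | Observed change (SD) | Power |
|---|---|---|
| 0 | 0.660 | 80% |
| 0.10 | 0.594 | 71% |
| 0.25 | 0.495 | 56% |
| 0.50 | 0.330 | 29% |

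The arithmetic is sound, but every input apart from n is assumed: f, the true change, and a paired t-test on an outcome the readable text does not name. The table shows what f would do; it gives no evidence that f exceeds zero.

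**4. Whether any text puts the scan on drug.**

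- No section ties a scan to the counted start. The counting rule defines treatment duration.
- Aim 1 uses the same before-and-after phrase for the OGTT. That baseline comes from routine care before enrolment, so it is pre-drug. The natural reading of Aim 2 is the same.
- Spironolactone is placed about two weeks into the study, so the study itself begins with metformin and 'before' points to a time ahead of it.
- Patients/Subjects excludes use of either drug in the previous six months, so participants enter off both.

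**5. What the readable text lacks.** Patients/Subjects, Observation and Measurements, Data Analysis, DATA Collection and the five numbered risks contain no scan procedure, outcome, analysis, eligibility rule or risk statement. The flow chart said to hold the complete design is not reproduced, and the Visit Flow heading has no visit schedule beneath it. It therefore cannot be claimed that paired scans are absent.

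**The case for a change.** The strongest case for a change is that Aim 2 is one of only two specific aims, yet nothing readable makes it operational. Because the counted intervention and the first drug exposure fall on different dates, a coordinator could scan after the first tablet and believe the protocol had been followed. One sentence would prevent that at almost no cost. Loss of text in the PDF conversion is an unlikely explanation for all the omissions: the risk list runs from 1 to 5 without a gap, and the questionnaire from the same rationale is carried into the measurement, data and risk sections. Even if the flow chart dates the scans, the funding wording fits a research baseline scan awkwardly.

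Part of this stands. The readable text does lack imaging detail, and the insurance sentence is loosely drafted. But that sentence belongs to a paragraph about routine-care data, and naming imaging funds beside post-intervention tests does not bar them from paying for a first scan. The coordinator's error requires an unnatural reading of 'before'. The alternative remedy, dropping Aim 2, would be justified only if paired scans were not planned, which the documents do not establish.

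**Conclusion.** No change to the plan follows. Two rules that serve other purposes, the treatment count and the billing of routine tests, are not scan-timing rules. Read plainly, Aim 2 calls for a scan before any study drug and another after treatment. What remains is missing detail on timing, measure and funding, which the investigators would settle sensibly when booking scans or which the unseen flow chart may already give.

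The size of the timing issue is at most 14 days of titration, 7.7% of six months, and then only if a scan were booked at the counted start. The fall in power from 80% to 29% applies only at an assumed f of 0.50; at f = 0 there is no loss, and the documents do not allow a choice between these values. The study is a single-centre, uncontrolled pilot with no hypothesis test stated for Aim 2. The primary outcome and its 93% power are untouched.

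This conclusion rests on the plain reading of 'before' and on not treating an unseen flow chart as an omission. If that chart scheduled the first scan after the first metformin tablet, or showed no paired scans, the question would need to be reopened.

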## B) BACKGROUND AND SIGNIFICANCE

PCOS is the most common and complex endocrinopathies in the female population. At the core of the condition lies an exaggerated ovarian/adrenal androgen production in response to physiologic and supra-physiologic elevations in insulin. Clinically, this hyperandrogenism is linked to acne, hirsutism, and menstrual irregularity. Additionally, hyperandrogenism positively feeds back onto insulin resistance, thereby perpetuating hyperinsulinemia. This becomes a vicious cycle, and it is this perpetuated insulin resistance that is deemed responsible for the detrimental metabolic sequelae of PCOS. Adverse outcomes include Type 2 diabetes, cardiovascular disease, depression, and obstructive sleep apnea (OSA). Adolescent PCOS treatment focuses on treating insulin resistance (i.e., metformin) with or without symptomatic/cosmetic relief through oral contraceptive hormones. However, studies seeking significant metabolic improvement by targeting both hyperandrogenism and insulin resistance are lacking.

Without treating hyperandrogenism in PCOS patients, insulin resistance remains. This is because the driving force behind the metabolic downward spiral is not shut down. Therefore, simultaneously targeting *both* insulin resistance and hyperandrogenism should be highly effective in improving biochemical markers of insulin resistance in adolescents with

PCOS. Indeed, reports in adolescents  indicate that hyperandrogenism is an important treatment target in the goal of improving metabolic health parameters. A recent study in adult women with PCOS demonstrated that the drug combination of low dose anti-androgen (spironolactone) and low dose insulin sensitizer (metformin) is superior to either drug alone in improving all metabolic parameters of PCOS . Remarkably, the metformin dose and spironolactone dose used in this study was lower than the usual recommended dose for mono-therapy in adolescents with PCOS.

Spironolactone has been used for decades as a potassium sparing diuretic and was found to have anti-androgenic effect in the 1970's . Its anti-androgenic effect is carried out through a dual mechanism of androgen receptor blockade, and via spironolactone's inhibition of 5-alpha reductase, thus reducing the conversion of testosterone to its biologically more potent metabolite, di-hydrotestosterone. The concern with studying spironolactone in adolescent girls has always been the potential effect of the drug to under-virilize a male embryo through transplacental exposure of the drug, should an unplanned pregnancy occur. However, unlike the widely prescribed OC, spironolactone does not pose a serious health risk (i.e thrombo-embolic events) to the patient herself  and therefore is the safer drug for the subject, especially if she is overweight and has a family history of thrombo-embolism events. Furthermore, a recent study in adolescent girls with hirsutism, demonstrated that a carefully designed study does not need to preclude adolescents from receiving anti-androgen therapy . In this study, adolescent girls with hirsutism were treated with the potent anti-androgen finasteride for 6 months and were not on oral contraceptive pills. In our proposed study, risk will be reduced by precluding sexually active teens from partaking in the study. Furthermore, all participants, even if not sexually active will be required to take a monthly pregnancy test for the duration of the study. This would likely safeguard against any inadvertent exposure of a male conceptus to spironolactone, as study drug would be discontinued immediately in the event of a positive pregnancy test. Lastly there has been a case report on a young woman treated with spironolactone (200-400mg daily) throughout each of her pregnancies due to Bartter Syndrome. In the case description she delivered two normal male infants and one normal female. At the time of the report one of the males had entered puberty at a physiologic time. While the teratogenic concern remains based on some, but not all animal studies carefully selected subjects and stringent protocol adherence should allow this very beneficial drug to be examined in adolescents with PCOS.

Metformin is well known for its insulin sensitizing effect at the level of the liver and its beneficial effect on diabetes prevention . In a double- blind placebo-controlled study in obese youth the principal investigator of the current proposal has shown that metformin is well tolerated in youth and has beneficial effects on BMI and autonomic control of the heart . Metformin use, especially in adolescents, is becoming an increasingly preferred treatment over oral contraceptive pills unless the patient is sexually active. In their 2013 guidelines on treating PCOS in adolescents, the Endocrine Society states that metformin has shown to restore menstrual regularity, improve hyperandrogenism and glucose tolerance in obese and non-obese patients . However, due to a lack of sufficient adolescent studies, the Endocrine Society's first line treatment recommendation remains oral contraceptive pills for PCOS in adolescents. The safety profile of metformin is excellent and the risk for lactic acidosis in patients with normal kidney function is no longer a concern for the medical community. Gastrointestinal side effects are not uncommon but can be overcome by taking the metformin with food and by starting with a low dose that is incrementally increased, titrated to tolerance.

### **C) PRELIMINARY STUDIES/EVIDENCE OF CAPABILITY**

The principal investigator has a longstanding history in clinical research in the field of adolescent obesity as it relates to metabolic and cardiovascular disease. She has specifically performed drug interventions with metformin  and studied adolescent girls with PCOS , giving her great expertise in proposed area of study. She has a track-record of publishing as first and senior author and has obtained NIH funding (K23).

At her prior employment she established and directed a successful multi-specialty adolescent PCOS program which allowed her to recruit 100 subjects for her study on oral glucose tolerance in adolescents with PCOS. Since her arrival at CMH last year, she has recreated a similar program at CMH's Broadway location. For the program [name] has established collaborations with adolescent medicine, radiology and nutrition services. All patients seen in her program have OGTT and ovarian ultrasound performed at the same day of their initial consultation. Patients and families enjoy the "one stop" complete evaluation. This model not only allows for streamline care but also makes it easier to offer studies that require these examinations.

[name] is becoming a nationally recognized expert in PCOS and was just selected to give the “Year in Review in PCOS” at the upcoming annual PES/PAS meeting. She has written chapters and reviews on the topic and is the education chair for the AES-PCOS society. She recently returned from presenting her data on ovarian ultrasound in adolescent PCOS at the AES-PCOS society in Italy.

[name] is a licensed clinical psychologist with advanced training in cognitive neuroscience and functional neuro-imaging. Her laboratory investigates how the human brain weighs risks and benefits of choices about food (i.e. pediatric eating behaviors), purchasing decisions (i.e., neuroeconomics), and adherence to medical regimens (i.e., pharmacologic interventions in neurologic populations).

Her research has revealed that obese youth demonstrate differential brain structural and functional profiles when compared to healthy weight youth. Specifically, in response to appetitive stimuli including food images, obese children exhibiting increased reactivity to food cues in limbic and paralimbic cortical regions. Equally disconcerting, these differences also extend to food advertising cues (i.e., fast food brand logos) with obese children having a more limbic response and lean children demonstrating more reactivity in the prefrontal cortex (PFC), a cortical region associated with self-control. Even in the resting state (without stimulatory food cues) the brain’s neurofunctional connectivity of obese children differs from that of lean children, with obese children demonstrate increased connectivity between cortical regions associated with reward and valuation. In regards of applying [name] findings to PCOS, nothing is known about neurofunctional response to external appetitive cues in PCOS. Even less is known as to how pharmacologic treatment (i.e. metformin and spironolactone), can directly or indirectly impact brain structure and function.

## **RESEARCH DESIGN AND METHODS**

### **Research Design and Procedures:**

The overall objective of this proposal is to determine if metabolic improvements occurs in adolescents with PCOS after a 6-month open label intervention with a low dose synergistic drug regimen of metformin (insulin sensitizer) and spironolactone (anti-androgen).

Initial data will be collected as part of the patient’s routine PCOS health care. Should a patient consent to the study this data will be used as baseline analysis. During the 6- month intervention study the subject will have a safety monitoring visit at 3 months into the intervention which will include blood work, complete examination and compliance history. All baseline examinations will be covered by insurance. All post intervention biochemical or other testing will be covered by study funds and [name] neuro-imaging start-up funds.

For complete study design: see flow chart at end of the RESEARCH DESIGN AND METHODS section.

### **Study Design:**

This is a single center clinical research study to obtain pilot data.

It is a non-controlled open label drug intervention study in a convenient sample of adolescent girls attending a PCOS clinic.

### **Patients/Subjects:**

The sample will include 20 adolescent females (ages 13-21) of all ethnic backgrounds referred to the CMH adolescent PCOS program for evaluation and management of PCOS.

Patient risks and safeguards are extensively described in PROTECTION OF HUMAN SUBJECTS

Inclusion Criteria: Generally healthy; Meeting Androgen Excess Society (AES) diagnostic criteria of PCOS: Menstrual Dysfunction or PCO ovaries on ultrasound AND clinical or biochemical hyperandrogenism.

Normal liver and kidney function. No chronic illnesses except for stable, treated hypothyroidism.

Exclusion Criteria: Use of metformin and/or spironolactone within the last 6 months. Currently on either oral hormonal contraception or other forms of hormonal contraception such as Depo-ProveraR, NuvaRingR

Current or past pregnancy; Currently sexually active; Psychiatric disorder based on self/parental report; type 2 diabetes (blood glucose > 200mg/dl on OGTT); Anemia (Hct < 35); Baseline creatinine > 1.0 mg; Abnormal liver transaminases > 2 x the upper limit of normal range, potassium elevated outside the reference range (in non-hemolyzed blood sample).

